BOLD fMRI pre-processing: After discarding the first 4 volumes for saturation effects, images will be corrected for movement with a 3-dimensional rigid body transformation. Participants with scan-to-scan head movement >2 mm will be excluded. Motion parameters will be modeled as nuisance variables. Images will be normalized to MNI space using the two step transformation procedure described for MR CBF. Images will be spatially smoothed with a 6 mm full-width-half-maximum isotropic Gaussian kernel, filtered to remove low-frequency fluctuations (128 s high pass filter), and corrected for temporal autocorrelation.

BOLD fMRI: Model specification and contrast of interest: The time series will be predicted by nine regressors, consisting of decision and outcome for each of the four decks, plus motor control. Motion parameters will be modeled as nuisance regressors. The stimulus function will be convolved with the canonical hemodynamic response function (HRF). We are primarily interested in effects of acetate or alcohol on brain activity during the decision phase of the task. The primary outcomes will be the contrast of Decision>motor control baseline and Outcome>motor control baseline. For each participant these contrast maps will be brought to the second level for subsequent ROI and whole-brain analyses.

Regions-of-interest (ROI): ROI and whole brain analyses will be conducted for outcome measures of CBF and fMRI BOLD activity. Six anatomically- defined ROIs will be based on the neural circuitry found to be involved during decision-making on the modified IGT and which overlap with brain regions showing altered signal after acute alcohol (Anderson et al., 2011; Bjork and Gilman, 2014). ROIs will be bilateral ventral striatum (VST), dorsal striatum, insula, and anterior cingulate cortex (ACC), orbitofrontal cortex (OFC), and dorsolateral prefrontal cortex (DLPFC). VST and DST will be manually drawn, based on published landmarks (Mawlawi et al., 2001). For the OFC, insula, ACC, and DLPFC, the automated anatomical labeling atlas (AAL) (Tzourio-Mazoyer et al., 2002) will be used. Figure 3 shows examples of VST=green, DST=orange, OFC=blue, insula=red.

[figure not shown]

Fig 3. Regions of interest

Statistical Analysis: We have three outcomes of interest: 1) CBF, 2) fMRI BOLD signal during decision-making, 3) behavioral measures. A bio-statistician employed part-time by the Department of Radiology will provide statistical support. The aim of this pilot study is simply to determine the feasibility of performing the experiment and to acquire the necessary data to calculate power needed for a larger study.

CBF: ROI analyses: For this feasibility pilot study, a paired t-test will be used to investigate the effect of acetate and the effect of alcohol separately. In an exploratory manner, drug x time interactions will be examined through descriptive and graphical analyses, though we acknowledge insufficient power to reject the null hypothesis of no interaction. Nevertheless, a noticeable difference in outcomes based on factors of drug or time could provide data to compute power for a larger, more powered study.

To provide context for this pilot, the statistical plan for the later, larger study is included: We will fit a general linear multivariate model with repeated measurements of CBF as the outcomes. Each participant will have 12 repeated measurements (6 ROIs x 2 treatments (acetate and placebo or alcohol and placebo)). Age and number of drinks per week will be included as covariates. MCMC imputation (Li, 1988) will be used to address missing data. A Chi-Muller test will be conducted (Chi and Muller, 2013) for the main effect of treatment (acetate versus placebo or alcohol versus placebo) at any ROI. Residual analysis will be used, and Box-Cox transformations will be considered to account for deviations from multivariate normality. An alpha spending approach will be used to handle multiple comparisons problems, by testing the overall hypothesis of no effect at any region at the $\alpha = 0.04$ level, and then, if we attain significance, testing the treatment effects at each ROI at the $\alpha = 0.01/6$ level. This yields a total Type I error for this aim of $0.05 = 0.04 + 6*(0.01/6)$.

CBF: Whole brain analyses: The main effects of acetate on CBF will be analyzed in SPM12 using a repeated-measures ANCOVA with drug (alcohol, or acetate vs. placebo) as within-subject factor and adjusting for age and number of drinks per month. As this is a feasibility study, a less stringent threshold of $p < 0.05$, uncorrected will be used to explore for possible main effects and interaction effects as well as nonparametric approaches. In the later, larger study, significance levels will be set at $p < 0.05$, corrected for multiple comparisons with family-wise error (FWE) using AlphaSim Monte Carlo simulations, 10,000 iterations, to determine cluster size criterion. The voxel-level significance will be set at $p < 0.005$.

fMRI BOLD activity: ROI analyses: For each ROI and each subject, the percent signal change will be extracted using Marsbar toolbox. The feasibility analyses are the same as CBF: ROI approach. To provide context for this pilot, the statistical plan for the later, larger study is included: To examine the main effect of alcohol or acetate on BOLD response, a general linear multivariate model with 12 repeated BOLD response measurements as the outcomes will be employed. Covariates will include education level and number of drinks per week. From prior experience, BOLD activity during decision-making correlates with education level. Analyses are otherwise the same as CBF: ROI approach.

fMRI BOLD activity whole brain analyses: The feasibility analyses are the same as CBF: whole brain analyses. In the later, larger study, the main effects of alcohol or acetate on fMRI BOLD signal during decision-making will be analyzed in SPM12 using a repeated-measures ANCOVA with drug (alcohol or acetate vs. placebo) as within-subject factor and adjusting for education and number of drinks per month. Analyses are otherwise the same as for the CBF: whole brain analyses.

Behavioral: Decision-making performance will be analyzed with repeated measures ANOVA on net score, adjusted for education level. Net score is the number of plays on good decks minus bad decks. The behavioral effects of treatment will be analyzed using repeated measures ANOVA on SHAS7, on the psychomotor vigilance task, simple and choice reaction time task, and grooved pegboard task.

Power and Confidence Interval Width: This study is a pilot study, designed to estimate the size of the effect, and provide accurate parameter estimates for a later, more definitive study. The power analysis here is based on the work of Schwartz et al. (Schwartz et al., 1993), who studied CBF before and after drinking and observed a mean difference in flow measured as a ratio of cortex/cerebellum (after – before) of 0.054 with standard deviation of the difference of 0.085. The smallest difference in CBF that a study with 10 people can detect using repeated measures ANCOVA with 90% power and a Type 1 error of 0.05 is a difference of 0.09 (ratio of cortex/cerebellum). Therefore we should have adequate power to detect a difference with alcohol. There is no prior CBF data on acetate in the literature to perform power analysis for acetate. This study is designed to provide preliminary data for a later study and an estimation of the N necessary for that study to provide sufficient power for analysis.

G. Summarize Knowledge to be Gained:

This proposal is relevant to public health because of the considerable impact alcohol has on the health of individuals and in terms of legal, medical, and social costs to the country. Again, this is a pilot study to determine the feasibility of measuring effects of oral alcohol and intravenous acetate on CBF and function in moderate drinkers and AUD individuals. Data from this study will be used to apply for funds to conduct a larger study. The results from this the later,

larger project will add to our knowledge about mechanisms of acute alcohol's effects on brain function and the role of acetate in these effects.

H. References:

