Acute alcohol is associated with increased cerebral blood flow (CBF). It is unknown if changes in CBF are due to alcohol, acetate, or both. Determining the differential effects of alcohol and acetate on brain function is significant as it could lead to new treatments targeting alcohol metabolites. The goal of the proposed study is to determine feasibility of measuring effects of oral alcohol and intravenous acetate on cerebral blood flow and function in moderate drinkers with the objective to use the data collected for an R01 or R21 application. Although currently there is no data in the literature on this, finding such changes would be important and could direct future prevention and treatment plans for alcohol use disorders. For this feasibility pilot study we propose to investigate the effects of acetate and alcohol on CBF and brain function with two specific aims.

Aim 1. Investigate the effects of acetate on cerebral blood flow and function in controls and AUD individuals

Preliminary data will be collected for the hypothesis that compared to placebo given IV acetate given IV will: a) increase CBF as measured by arterial spin labeling (ASL); and b) decrease blood oxygen level dependent (BOLD) activity during functional magnetic resonance imaging (fMRI); and c) these changes will be greater in AUD individuals than controls

Aim 2. Investigate the effects of alcohol on cerebral blood flow and function in controls and AUD individuals

Preliminary data will be collected for the hypothesis that compared to non-alcoholic jello shots, orally ingested alcohol jello shots will: a) increase CBF, and b) decrease BOLD activity; and c) these changes will be greater in AUD individuals than controls.

II. Background and Significance:

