Practice effects: It is possible that differences in brain activity could reflect learning effects. To test for learning effects we administered two versions of the decision-making task to a healthy control, 2 hours apart. The two versions differed in the color and position of the decks and the scale of the magnitude of outcomes, while keeping the value of the decks balanced. The frequency of wins and losses was identical. There was no difference in Play response on good cards (93 vs. 95), bad cards (54 vs. 55), or on net score (good minus bad cards played) (39 vs. 40). *This lack of significant practice effect is consistent with a prior study showing stable performance on the Iowa Gambling Task, on which our task is based, given multiple times to controls (Xiao et al., 2013) and patients (Waters-Wood et al., 2012) and, together, suggest that there will not be a significant learning effect.*

IV. Research Methods

A. Outcome Measure(s):

Our goal in this pilot study is feasibility.

Preliminary outcome measures:

1. CBF before and after acute alcohol or acetate
2. Brain activity during decision-making before and after acute alcohol or acetate

B. Description of Population to be Enrolled:

This is a single blinded placebo controlled test of the effects of acetate and alcohol on brain function.

Inclusions-all: (1) age 21-55, (2) English proficient, (3) Participants must understand the nature of the study and must sign an informed consent; (4) be currently non-smoking.

Inclusions-moderate drinkers: (1) participants must be moderate drinkers (male: 1-14 drinks per week; female: 1-7 drinks per week); and (2) have drunk at least 2 drinks in one hour in the past; and have no history of dependence on drugs or alcohol.

Inclusions-AUD: (1) must meet DSM-V criteria for lifetime history of Alcohol Use Disorder (AUD)

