Exclusions-all: Participants will be excluded if they: (1) have a “facial flushing” response to alcohol; (2) are pregnant or nursing; (3) have major medical problems including diabetes, uncontrolled high blood pressure (> 150/90), prior neurological or psychiatric history (schizophrenia, bipolar, or current major depressive disorder, epilepsy (alcohol withdrawal seizures is not an exclusion)); (4) have ever been told they have or been diagnosed with liver or kidney disease; (5) have a diagnosis of chronic gastrointestinal disease; (6) are obese (BMI>30 kg/m²); (7) have prior head trauma resulting in loss of consciousness>15 min.; (8) have MR exclusions which include claustrophobia, intracranial, orbital, or spinal metal, pacemakers, cochlear implants, cardiac stents or other non-MR-compatible implants or devices.

C. Study Design and Research Methods

Study Design

This is a pilot study to determine the feasibility of measuring effects of acetate alone and acetate obtained as a byproduct of alcohol metabolism on CBF and brain activity. Our recruitment goal will be 50 subjects: 40 healthy controls who are social drinkers (1-14 drinks per week) to achieve a target of n=20 scanned for Aim 1 and n=20 scanned for Aim 2, with a final usable healthy control target of n=15 for Aim 1 and n=15 for Aim 2 (a few subjects may not qualify for data analysis due to excessive head motion in scanner); and 10 AUD individuals, to achieve a target of n=7 scanned for Aim 1. AUD participants seeking treatment will be excluded from Aim 2 (alcohol arm). Moderate drinkers will be recruited through advertisements and flyers. AUD subjects will be recruited from the Center for Dependency, Addiction and Rehabilitation (CeDAR) at the University of Colorado Anschutz Medical Campus.

Order effects: Before the study commences, test-retest reliability will be conducted on two healthy controls on MR measures by scanning them twice in a single day, with no intervention. The null hypothesis of no difference in brain activity and CBF will be tested, between the two sessions. Notably, the literature shows high reliability for test-retest of CBF using ASL at various time intervals (Floyd et al, 2001, Chen et al., 2011).

Session 1: Consent and diagnostic assessment (total time ~1 hour)

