Potential participants will take part in a short interview at the Anschutz Medical Campus consisting of explanation of the study, screening for MRI compatibility, signing informed consent, and answering questions on drug and alcohol use.. Control participants will be randomized to the acetate or alcohol branch of the study but will not know which branch they are assigned to until Session 2. AUD participants will be assigned only to the acetate branch of the study. Participants will be asked to not drink alcohol for 48 hours prior to the study and to eat a light low-fat breakfast before coming to the University for Session 2. Session 2 (scan day) will be scheduled as soon as possible, about 1-2 weeks after Session 1.

Questionnaires:

- (1) Composite International Diagnostic Interview Substance Abuse Module (CIDI-SAM). Dependence on alcohol, cannabis and nicotine will be measured using the computerized CIDI-SAM, a structured interview designed for trained, lay interviewers (Cottler et al. 1995). (30 min)
- (2) Alcohol Use Disorders Identification Test (AUDIT). This test screens for alcohol abuse and average alcohol use (5 minutes)
- (3) Timeline Followback assessment. This assessment measures frequency and quantity of alcohol consumption for the most recent 1-3 months of alcohol use.

Session 2: Acetate or Alcohol and MRI scanning (~7 hours)

Research participants will arrive at the Clinical and Translational Research Clinic (CTRC) in the Leprino Building on the University of Colorado Anschutz Medical Campus (AMC) at 7:30 am, turn in their stool samples and 2 day food log, and provide urine samples to screen for alcohol, drugs and pregnancy.

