E. Potential Scientific Problems:

1. Sex effects: Alcohol metabolism differs in men and women and several studies find an interaction between sex and alcohol's effect on terms of brain morphometry (Hommer et al., 2001), function, and CBF (Marxen et al., 2014; Rickenbacher et al., 2011). It should be noted, however, that not all studies have confirmed sex differences in brain morphometry (Demirakca et al., 2011). There will not be power to detect sex effects. Our goal is to demonstrate feasibility.

2. Vasomotor effect: The BOLD signal reflects complex interactions between CBF, cerebral blood volume, and oxygenation. We plan to study differences in global and regional vascular effects in acetate vs. alcohol treatment. The fMRI BOLD measurements are insensitive to time lags or shifts in the hemodynamic response of the brain during decision-making. Therefore in exploratory studies a finite impulse response (FIR) model will be used, according to prior work (Yamamoto et al., 2014).

3. Diurnal variations: We cannot exclude the possibility of diurnal fluctuations confounding our findings. The alternative to conduct blinded placebo and treatment studies on two separate days in the same participant would be a hardship on participants.

4. Dose-response: A dose-response for acetate or alcohol will not be obtained. Fortunately, the pharmacokinetics of alcohol are well established and the timing of the MR scans is planned according to Figure 2. The pharmacokinetics of acetate are not as well established. The IV infusion protocol will give us better control of plasma levels, and serum acetate and alcohol will be assayed.

F. Data Analysis Plan:

Blood alcohol and acetate: Levels of blood alcohol and acetate will be analyzed using colorimetric enzyme-linked immunosorbent assays (ELISA).

MR measures: MR CBF and fMRI BOLD activity data will be processed in SPM12 (The FIL Methods Group, 2014). First, each participants' T1-weighted anatomic image will be skull-stripped then coregistered to the Montreal Neurological Institute (MNI) MNI152 template. The transformation matrix generated from this step will be applied to CBF and BOLD contrast maps of interest.

MR CBF: Motion-corrected ASL CBF images (mL/100g/min) will be generated by the scanner software. CBF maps will be skull-stripped and co-registered to each participant's T1-weighted anatomic image in native space followed by application of the transformation matrix to MNI space.

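### Hypothesis 2c has no planned AUD participants under alcohol, and hypothesis 1c has planned data but no AUD-versus-control analysis

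*Combined protocol and SAP*

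**What the plan says.** Section I defines the second aim as "Aim 2. Investigate the effects of alcohol on cerebral blood flow and function in controls and AUD individuals". It promises preliminary data for three hypotheses under that aim, the last two being that alcohol will "b) decrease BOLD activity; and c) these changes will be greater in AUD individuals than controls". Aim 1 makes the same third claim for acetate (1c).

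Three statements in Section IV.C bear on who receives what:

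- Study Design, on exclusion: "AUD participants seeking treatment will be excluded from Aim 2 (alcohol arm").
- Study Design, on numbers: "10 AUD individuals, to achieve a target of n=7 scanned for Aim 1". The 40 controls are split 20 and 20 across the aims, "with a final usable healthy control target of n=15 for Aim 1 and n=15 for Aim 2". The total is 50.
- Session 1, on assignment: "AUD participants will be assigned only to the acetate branch of the study". Only controls are randomised between branches.

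The analyses listed in Section IV.F for the pilot are:

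- a paired t-test for each drug separately (ROI analyses of CBF, and the same for BOLD);
- descriptive drug-by-time displays;
- a whole-brain repeated-measures ANCOVA with drug as the within-subject factor and covariates (age and drinks per month in the CBF version), with interaction effects mentioned but not named;
- repeated-measures ANOVAs for the behavioural measures.

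Section IV.E, item 2, adds: "We plan to study differences in global and regional vascular effects in acetate vs. alcohol treatment".

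**The concern.** The pilot's stated product is the information needed to power a larger study. For 1c and 2c that means the AUD-minus-control difference in the drug effect and the SD of change in each group. As written, 2c receives no AUD data at all. For 1c the scans will exist, but following Section IV.F to the letter produces no group contrast.

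A second gap follows from the first. Section IV.F does not say whether AUD participants and controls are combined or kept apart in the acetate t-test. If they were combined, the acetate sample would contain AUD participants and the alcohol sample would not. The descriptive acetate-versus-alcohol comparison foreseen in Section IV.E would then differ by AUD status as well as by drug, and the randomisation of controls between branches would no longer protect it.

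**Working it through.** **The plan's own power figure.** Section IV.F (Power and Confidence Interval Width) gives a detectable difference of 0.09 with 10 people, 90% power and Type 1 error 0.05, from an SD of the difference of 0.085. With a two-sided normal approximation: (1.960 + 1.282) × 0.085/√10 = 0.087, which rounds to 0.09. The figure reproduces on that basis (a two-sided t calculation gives 0.098). It describes a within-person change in one group and says nothing about an AUD-versus-control difference.

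**Hypothesis 2c: head count.** 20 controls (Aim 1) + 20 controls (Aim 2) + 10 AUD (Aim 1) = 50, which is the whole recruitment goal. AUD participants left for alcohol: 0. The Study Design exclusion covers only treatment-seeking AUD participants and so is narrower than the Session 1 rule. Even on that reading no AUD number is planned for alcohol, and the only AUD recruitment source named is a rehabilitation centre.

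**Hypothesis 1c: search for a group term.** None of the ROI, whole-brain or behavioural analyses names AUD status as a factor, and neither do the models described for the later study. Drinks per month does not stand in for it, because AUD participants "must meet DSM-V criteria for lifetime history of Alcohol Use Disorder (AUD"), a lifetime criterion applied to people recruited from rehabilitation.

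**Hypothesis 1c: precision if the contrast were added.** Take the difference between groups in change score (acetate minus placebo), in units of the SD of change, assuming equal SDs and using Welch degrees of freedom:

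- SE = √(1/n₁ + 1/n₂)
- df = (1/n₁ + 1/n₂)² / [(1/n₁)²/(n₁−1) + (1/n₂)²/(n₂−1)]
- 95% half-width = t(0.975, df) × SE

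No usable AUD target is stated. The second row assumes AUD scans are lost at the controls' planned rate: 7 × 15/20 = 5.25, taken as 5.

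| Controls vs AUD | SE | df | t | Half-width | Detectable, 80% power |
|---|---|---|---|---|---|
| 15 vs 7 | 0.458 | 11.8 | 2.183 | 1.00 SD | 1.40 SD |
| 15 vs 5 | 0.516 | 6.9 | 2.372 | 1.22 SD | 1.69 SD |

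The detectable differences come from the noncentral t distribution, two-sided at 0.05. If the AUD group's SD of change were 1.5 times the controls' (assumed), the half-widths would be 1.42 and 1.82 control SDs.

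To put this on the scale of the power section, assume its SD of 0.085, observed under alcohol as a cortex/cerebellum ratio, also held for acetate:

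- 15 vs 7: 0.999 × 0.085 = 0.085, and 0.085/0.054 = 1.6
- 15 vs 5: 1.225 × 0.085 = 0.104, and 0.104/0.054 = 1.9

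The interval's half-width would be 1.6 to 1.9 times the whole cited mean change of 0.054.

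**AUD share of the acetate sample if the groups were combined.** Scanned: 7/27 = 26%. Usable at the assumed loss: 5/20 = 25%. No AUD loss against 15 usable controls: 7/22 = 32%. Alcohol sample: 0%.

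**The case against.** The best reply is that this is a feasibility pilot promising only preliminary data. On that view the Aim 2 problem is a wording slip that cannot produce a wrong result, since a contrast with no AUD participants cannot be run. If everyone recruited from the rehabilitation centre is seeking treatment, the two Section IV.C rules agree in practice. For 1c, group means and SDs can be computed from the collected scans without a pre-named test, and the open-ended mention of interaction effects leaves room for one. The pooling worry is conditional: the plan never says the groups will be combined, and the Section IV.E sentence is a caveat, not a defined contrast. Finally, a pooled-variance t-test gives narrower intervals under the same equal-SD assumption.

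Parts of this stand. Low power for 1c is no fault in a pilot. The two Section IV.C rules may coincide in practice, though that does not supply data for 2c. The pooling point is a conditional risk. The 1c estimate is recoverable from the data, so what is missing is its specification. The pooled-variance half-widths are 0.955 SD (15 vs 7) and 1.085 SD (15 vs 5), or 0.081 and 0.092 on the ratio scale, against 0.085 and 0.104 with Welch. The choice of method does not change the conclusion. The unnamed interaction effects do not fill the gap, because the model they belong to has no between-group factor.

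**Conclusion.** The concern holds. Hypothesis 2c is stated as an object of data collection but has 0 planned AUD participants. Hypothesis 1c has planned data but no planned contrast. If the 1c contrast is added, its 95% half-width is about 1.0 to 1.2 SD of the change score, so it can only be exploratory. That range rests on equal SDs in the two groups and, at its upper end, on an assumed loss of AUD scans; the conversion to ratio units also assumes that the alcohol SD applies to acetate. The 25–32% AUD share applies only if the groups are combined, on which the plan is silent. The within-control questions (1a, 1b, 2a, 2b) are unaffected. This should be fixed, but it does not threaten the whole study.

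**What to change.** 1. Reconcile Section I (Aim 2), Section IV.C Study Design and Section IV.C Session 1, so that the aim matches the assignment actually used. Which assignment rule applies is for the investigators to settle. If the Session 1 rule stands as written, take AUD individuals and 2c out of Aim 2, or mark 2c as a hypothesis for the later study.
2. State in Section IV.F that the acetate paired analyses are reported separately for controls and AUD participants.
3. For 1c, report for each ROI the AUD-minus-control difference in change (acetate minus placebo) with a Welch 95% confidence interval, labelled exploratory, together with the SD of change in each group for planning the later study.
4. Restrict any descriptive acetate-versus-alcohol comparison to the randomised controls.

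The cost is protocol wording and a few lines of analysis, with no added participants or scans. The price is dropping or deferring a claim the design cannot support, and showing a wide interval for 1c.

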Decision-making task (Fig 2): Participants will play a modified version of the Iowa Gambling Task (Bechara et al., 1994) during fMRI scanning. The modified IGT assesses risk avoidance and sensitivity to negative outcomes (Tanabe et al., 2013; Thompson et al., 2012). We have many years of experience giving the task to substance users and controls. Briefly, participants are presented four decks of cards and instructed to earn as much hypothetical money as possible by choosing to either Play or Pass on a given deck. “Play” results in a single positive or negative monetary value, along with the running total. “Pass” results in no change. To perform well, participants must learn to Pass on the two bad decks that result in a net loss and Play on the two good decks that result in net gain over time. The payout of the decks is controlled on the frequency and magnitude of wins and losses. The decision period is 2 seconds, and the outcome period is 4 seconds, separated by a variable jitter of 0 to 4 seconds. There are 50 trials of each deck, 200 trials total, plus 40 baseline trials to control for motor effects, and 10 six-second fixation crosses presented in pseudorandom order. Total task scan time is 24 minutes consisting of two 12 minute runs. The task will be given twice, once in the morning and once in the afternoon. To reduce practice effects for the afternoon study, the color, win/loss amounts (but not the ratio of wins:losses), and the order of the decks will be changed.

[figure not shown]

Figure 3. Decision-making task and timing parameters.

D. Description, Risks and Justification of Procedures and Data Collection Tools:

Session 1

1. Consent Procedures: Participants will have time to ask questions and have the study explained by PI. They will fill out an MRI screening form to ensure safety prior to entrance to the scanner.
2. The session will be conducted in a private room to facilitate confidentiality. Data collected during the initial screening and between and after the MR sessions will be associated with the participant number only and will assess alcohol use (frequency, amount, and abuse/dependence symptoms).
3. Participants will be paid \$35 for completing Session 1.

Session 2

1. Participants will be asked to not drink alcohol for 48 hr prior to Session 2 and to eat a light low-fat breakfast on the day of Session 2 to avoid interference with alcohol absorption.

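### Controls are screened for past dependence while cases are defined by lifetime AUD, so one person can meet both group definitions

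*Combined protocol and SAP*

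**What the plan says.** **Group definitions (section IV.B, Description of Population to be Enrolled).** For controls, "participants must be moderate drinkers (male: 1-14 drinks per week; female: 1-7 drinks per week"). They must also have had at least two drinks within an hour at some time, "and have no history of dependence on drugs or alcohol". An AUD participant "must meet DSM-V criteria for lifetime history of Alcohol Use Disorder (AUD"). No severity, current-use or dependence requirement is added for the AUD group.

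**Instruments (section IV.C, Session 1, Questionnaires).** "Dependence on alcohol, cannabis and nicotine will be measured using the computerized CIDI-SAM". Of the AUDIT the plan says: "This test screens for alcohol abuse and average alcohol use". It gives no AUDIT cut-off and no eligibility role for the score. Timeline Followback covers the most recent 1-3 months. Section IV.D says that the data collected "will assess alcohol use (frequency, amount, and abuse/dependence symptoms").

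**Allocation and numbers (section IV.C, Study Design and Session 1).** Controls are randomized to acetate or alcohol, with a "final usable healthy control target of n=15 for Aim 1 and n=15 for Aim 2". AUD participants go only to the acetate branch, where 7 are to be scanned. Controls come through advertisements and flyers, and AUD participants from a rehabilitation center.

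**Hypothesis (section I, Aim 1, part c).** The plan expects that "these changes will be greater in AUD individuals than controls".

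**The concern.** A comparison of people with and without a disorder needs one definition, applied as present in one group and absent in the other. Here the case group is defined by AUD and the control group by the absence of dependence. If dependence is narrower than AUD, the definitions leave an overlap: people with lifetime AUD who were never dependent and whose present drinking is moderate.

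Two things are at stake. First, such people enrolled as controls would make the control group resemble the AUD group, so the contrast behind hypothesis 1c would be underestimated. The Power and Confidence Interval Width paragraph says that the pilot is meant to supply accurate estimates for a later study, so a bias in a descriptive contrast still matters. Second, a person who meets the AUD definition but is enrolled as a control enters the randomization and may be allocated to alcohol, contrary to the Session 1 statement on AUD participants.

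**Working it through.** **Step 1: can one person satisfy both definitions?** Take someone with a lifetime DSM-V AUD history, never dependent, now drinking 1-14 (male) or 1-7 (female) drinks per week.

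| Rule | Place | Keeps this person out of the controls? |
|---|---|---|
| Weekly drinking range | IV.B, moderate drinkers | No; it concerns present intake |
| No past dependence | IV.B, moderate drinkers | No, by construction |
| Exclusions for all | IV.B | No; neither AUD nor alcohol abuse is listed |
| AUDIT | IV.C, Questionnaires | No; no threshold stated |
| Timeline Followback | IV.C, Questionnaires | No; recent months only, no threshold stated |
| Recruitment source | IV.C, Study Design | No; it is not an eligibility rule |

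The same person meets the only inclusion specific to the AUD group. No rule makes the groups mutually exclusive.

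**Step 2: does the plan treat dependence as the same thing as AUD?** It never says so. It describes the CIDI-SAM as measuring dependence and the AUDIT as screening for abuse, and section IV.D names abuse and dependence symptoms side by side. The natural reading is that dependence is the narrower term.

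**Step 3: where does the contrast exist?** Only in the acetate branch, with 15 usable controls and 7 scanned AUD participants. No usable number is given for the AUD group.

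**Step 4: size.** The documents give no figure for an AUD-control difference or for the share of controls affected. The only power figure is a detectable within-person change of 0.09 with 10 people. It reproduces by the two-sided normal formula, 0.085 × (1.960 + 1.282) / √10 = 0.087, and has no bearing on this point.

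Let k of 15 controls have AUD, and let each respond a fraction f of the way from the control mean to the AUD mean. The expected contrast, as a share of the true one, is

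retained = 1 − f × k/15.

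Both k and f are assumptions.

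| k | f = 1 (respond like the AUD group) | f = 0.5 |
|---|---|---|
| 1 | 1 − 1/15 = 93% | 97% |
| 2 | 1 − 2/15 = 87% | 93% |
| 3 | 1 − 3/15 = 80% | 90% |

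For f between 0 and 1, the f = 1 column is the greatest dilution for each k. At k = 0 nothing is lost.

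**Step 5: comparison with imprecision.** With equal SDs, the standard error of the contrast is √(1/15 + 1/7) = 0.46 SD. The 95% half-width, with t = 2.086 on 20 degrees of freedom, is about 0.95 SD. For an assumed true difference of 0.5 to 1.0 SD, losing 1/15 to 3/15 of it is a bias of 0.03 to 0.20 SD.

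**Step 6: allocation.** Session 1 randomizes controls to either branch and assigns AUD participants only to acetate. Study Design excludes from Aim 2 only those AUD participants who are seeking treatment. A person with AUD enrolled as a control falls under the first rule by group label and under the second by diagnosis.

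**The case against.** The strongest reply is that dependence is loose shorthand for the disorder. Section IV.D speaks of questions asked in order to rule out or diagnose substance dependence, which uses one term for both purposes. The CIDI-SAM is the only diagnostic interview named, so one interview may separate the groups in practice. Study Design also calls the controls healthy. This makes the loose reading possible, but it does not equate the terms: staff who apply section IV.B as written could properly admit the person described. It is also true that the plan nowhere states that AUD can be met without dependence. That is inferred from its separate naming of abuse and dependence.

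The second reply is that the bias is small beside the sampling error of 15 against 7, and that the stated goal is feasibility. Step 5 bears out the first part. It limits the importance of the point without closing the gap.

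A reader might go further in three ways that the documents do not support:

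- **Hypothesis 2c is also diluted.** Aim 2 states the same expectation, but AUD participants enter only the acetate branch, so there is no AUD-control contrast in the alcohol branch to bias.
- **The larger study would be mis-sized.** If 10% or 20% of controls were affected, the usual factor 1/(1 − p)² would give 1.23 or 1.56 times the sample size. That applies to an AUD-control test, and section IV.F plans none. The pilot uses paired tests, the later study's model tests the main effect of treatment, and the power paragraph rests on a within-person change.
- **The factor 1 − k/15 is the expected loss.** It needs a never-dependent moderate drinker to respond like a participant from a rehabilitation center. A milder response loses less.

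**Conclusion.** The point holds as a gap in the group definitions. As written, the control criterion can admit a person with lifetime AUD, and that person can then be randomized to alcohol despite the Session 1 assignment of AUD participants to acetate alone.

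The statistical consequence is confined to the descriptive contrast for hypothesis 1c, and its direction is toward zero. Its size is unknown and may be nil. With 1 to 3 of 15 controls affected, the contrast would keep at least 93% to 80% of its true value. This rests on an assumed number of misplaced controls and on their responding, at most, like the AUD group. The planned within-subject tests are not called into question. The change is worth making because it is cheap and because the pilot is intended to supply estimates for later planning.

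**What to change.** Replace the dependence clause in the control inclusion with: no lifetime history of AUD by the same DSM-V criteria used for the AUD group, and no history of drug dependence.

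Add a sentence to Session 1 stating that AUD status in both groups is derived from the abuse and dependence symptoms already collected there. The sentence is needed because the CIDI-SAM is at present described only as measuring dependence, and no instrument is named as establishing AUD.

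In the same amendment, reconcile the Session 1 allocation text, the Study Design exclusion from Aim 2 and the revised control criterion, so that diagnosis and group label cannot point to different branches.

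The cost is one eligibility line, one sentence on how AUD is established, and a few more control screen failures to replace. For controls already enrolled, the symptom data can be used to report the 1c contrast with and without anyone who meets the AUD definition, at no extra data collection.
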